## Study Protocol/Methods

We conducted a randomized clinical trial at a single tertiary care center in central Massachusetts from March 2021 until April 2023. Prior to study initiation, approval was obtained from the University of Massachusetts Chan Medical School institutional review board. Written informed consent was obtained from all participants before enrollment and patient safety data and trial progress was assessed via a Data Safety Monitoring Board with all reporting following Consolidated Standard of Reporting Trials guidelines.

Inclusion criteria included pregnant patients aged 18 years or older with a known diagnosis of T1DM that were managed with CSII/insulin pump. All included participants had to obtain pregnancy and delivery care the study institution and had to be able to provide written informed consent in English or Spanish. Patients were not eligible if they were under the age of 18 years old, had multiple gestations, had altered state of consciousness intrapartum, were critically ill requiring intensive care unit admission, at risk for suicide, presented with diabetic ketoacidosis on admission for delivery, had an intrauterine fetal demise prior to labor, fetal anomalies, or if the participant was unable to partake in their own care.

All eligible participants were approached antenatally during routine prenatal care and consented for participation. Participants were then randomly allocated to either continuation of an intrapartum CSII/insulin pump or intravenous insulin infusion. Permutated block randomization with varying blocks sizes was used to stratify randomization by intrapartum glycemic management strategy (CSII vs. IV). The resulting group allocations were kept in sealed, opaque envelopes until opened by the provider at the time of randomization. Patients and providers were not blinded to randomization given active participation of providers and patients was needed in both study arms. Once admitted for labor, two separate intrapartum glycemic protocols were followed based on randomization category (Supplementary Figures 1 and 2).

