All medical records were reviewed for maternal demographics, clinical characteristics, and perinatal outcomes including primary and secondary outcomes. The primary outcome for the study was the first neonatal blood glucose level measured after birth. At our institution, it is policy that all neonates of mothers diagnosed with pre-gestational diabetes receive a heel-stick glucose measurement within the first 2 hours of life. Neonatal hypoglycemia was defined as blood glucose level less than 40 mg/dL, which prompts treatment and further monitoring at our study institution. In order to detect a 10 mg/dL difference in mean neonatal blood glucose levels between groups with a type 1 alpha error of 0.05 and 80% power with equal group sizes, 35 participants in each group were needed for a total sample size of 70 patients.

Secondary neonatal outcomes included mean neonatal glucose in the first 24 hours of life, neonatal hyperglycemia treatments including oral or intravenous treatment, 5 minute APGAR less than 7, NICU admission, neonatal birthweight, neonatal birthweight meeting large for gestational age criteria by Fenton growth calculator for preterm infants or World Health Organization growth calculator for term infants, or additional adverse neonatal outcomes including respiratory distress requiring intubation or continuous positive airway pressure (CPAP), hyperbilirubinemia, and neonatal cooling. Maternal secondary outcomes included intrapartum hypoglycemic events defined as blood glucose less than 60 mg/dL, intrapartum severe maternal hyperglycemic events defined as blood glucose greater than 200 mg/dL, development of diabetic ketoacidosis intrapartum, mode of delivery, shoulder dystocia at delivery, development of gestational hypertension or pre-eclampsia, maternal blood transfusion, and maternal intensive care unit admission.

All summary data were collected and managed using REDCap tools hosted at UMASS Chan Medical School. Summary data are reported as frequencies for categorical variables and

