mean (standard deviation) or median (interquartile range) for continuous variables. All categorical variables were compared using Fisher exact test and Chi square testing where appropriate, while continuous variables were assessed for normality and t-tests or Wilcoxon rank sum tests were used where appropriate. For all analyses, a two-sided significance level of  $P<0.05$  was considered statistically significant. Analyses were performed using STATA/SE 17.0 (StataCorp, College Station, TX).

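### The unadjusted P<0.05 rule labels any of 17 secondary outcomes statistically significant, with no order, adjustment or exploratory status

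*Combined protocol and SAP*

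**What the plan says.** All references are to the combined protocol and SAP, section Study Protocol/Methods.

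- **Primary outcome.** One is named: "The primary outcome for the study was the first neonatal blood glucose level measured after birth". The sample size of 35 per group is built on it alone (10 mg/dL difference, alpha 0.05, 80% power).
- **Secondary outcomes.** The next paragraph lists neonatal outcomes, among them "neonatal hyperglycemia treatments including oral or intravenous treatment", and maternal outcomes, among them "mode of delivery, shoulder dystocia at delivery, development of gestational hypertension or pre-eclampsia". No order of testing, adjustment or exploratory label is attached to them.
- **Tests.** "All categorical variables were compared using Fisher exact test and Chi square testing where appropriate". For continuous variables, "t-tests or Wilcoxon rank sum tests were used where appropriate".
- **Significance rule.** "For all analyses, a two-sided significance level of" P<0.05 "was considered statistically significant". No outcome is exempted.
- **Reporting.** The trial is to be reported "with all reporting following Consolidated Standard of Reporting Trials guidelines". The text does not say what that implies for secondary outcomes. It promises group summaries (frequencies, means with SD, medians with IQR) but no between-group estimate or confidence interval.

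**The concern.** The plan states its labelling rule explicitly. It extends the words statistically significant to every secondary comparison at the threshold used for the powered primary test. With 17 such comparisons, a chance difference somewhere in the list is fairly likely, and the rule as written would let it be reported as significant.

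Several listed outcomes, such as NICU admission and maternal hypo- and hyperglycemia, could influence a reader's view of pump against intravenous insulin. The primary conclusion is not at risk. What is at stake is how much weight a secondary difference may be given.

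**Working it through.** **1. The plan's own figure.** The only design calculation is 35 per group for the primary outcome. With n = 2(1.960 + 0.842)² × SD² / 10², the result depends on an SD that the text does not give. Solving for n = 35 gives SD = 10 / (2.802 × √(2/35)) ≈ 14.9 mg/dL. The plan states no familywise error rate to reproduce. The figure carried forward is 35 per arm.

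**2. Count of secondary outcomes.**
- Neonatal, 9: mean 24-hour glucose, glycemia treatment, low 5-minute Apgar, NICU admission, birthweight, large for gestational age (LGA), respiratory distress, hyperbilirubinemia, cooling.
- Maternal, 8: hypoglycemia, severe hyperglycemia, ketoacidosis, mode of delivery, shoulder dystocia, hypertensive disorder, transfusion, ICU admission.
- Total 17: 2 continuous (24-hour glucose, birthweight) and 15 treated as binary (mode of delivery taken as two categories). Splitting a composite would shift the count slightly.

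**3. False-positive rate of each test.** The continuous tests are taken at 0.05. For a binary outcome with the same event rate in both arms, the exact probability of P<0.05 at 35 per arm is:

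| Event rate | Fisher | Chi-square if expected counts ≥5, else Fisher |
|---|---|---|
| 1% | <0.0001 | <0.0001 |
| 2% | 0.0001 | 0.0001 |
| 5% | 0.0026 | 0.0027 |
| 10% | 0.0130 | 0.0188 |
| 20% | 0.0252 | 0.0461 |
| 30% | 0.0278 | 0.0505 |
| 40% | 0.0280 | 0.0484 |
| 50% | 0.0240 | 0.0429 |

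**4. Assumed event rates (low / middle / high).** The documents give none.
- Neonatal glycemia treatment, NICU, LGA, hypertensive disorder: 20 / 40 / 50%
- Mode of delivery: 40 / 50 / 50%
- Hyperbilirubinemia, maternal hyperglycemia: 20 / 30 / 40%
- Respiratory distress, maternal hypoglycemia: 10 / 20 / 30%
- Low Apgar, shoulder dystocia, transfusion: 2 / 5 / 10%
- Ketoacidosis: 1 / 2 / 5%
- Cooling, ICU admission: 1 / 1 / 2%

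**5. Chance of at least one P<0.05, independent tests.** The formula is 1 − Π(1 − αᵢ). For the middle set:
- Fisher: 1 − 0.95² × 0.972⁴ × 0.976 × 0.9722² × 0.9748² × 0.9974³ × 0.9999 ≈ 0.299. Expected false positives, Σαᵢ = 0.35.
- Mixed rule: 1 − 0.95² × 0.9516⁴ × 0.9571 × 0.9495² × 0.9539² × 0.9973³ × 0.9999 ≈ 0.424. Expected false positives, 0.54.

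**6. Across sets and correlation.** Correlated results are simulated with a shared patient-level latent factor and LGA as a cut-off of birthweight.

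| Set | Fisher: independent / 0.5 / 0.7 | Mixed rule: independent / 0.5 / 0.7 |
|---|---|---|
| Low | 0.267 / 0.224 / 0.196 | 0.377 / 0.320 / 0.277 |
| Middle | 0.299 / 0.242 / 0.209 | 0.424 / 0.349 / 0.299 |
| High | 0.316 / 0.257 / 0.221 | 0.443 / 0.365 / 0.310 |

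**7. Reading of the treatment outcome.** The figures above take the treatment item as a common glycemia-treatment outcome. Read literally as treatment for hyperglycemia, at an assumed 1%, the middle independent figures become 0.279 and 0.394. The lowest case (low set, correlation 0.7, Fisher) becomes 0.183. The range is therefore about 18% to 44%.

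**8. Sensitivity.** If all 15 binary outcomes shared one rate between 2% and 50%, the same two test rules give about 10% (0.098) to 59% (0.585). The 18% to 44% range is therefore not a bound.

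**The case against.** The strongest reply is that unadjusted secondary outcomes are conventional. The plan ranks its outcomes, powers only one, calls the rest secondary, and claims no familywise control. All of that stands. A reader might infer that the plan gives secondary results equal standing with the primary; it does not, because the hierarchy is stated. What remains is that the significance label itself carries no exception, and nothing in the text limits what may be concluded from it.

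A reader might also infer a larger risk.
- Seventeen independent tests at exactly 5% would give 1 − 0.95¹⁷ = 58%, but rare outcomes at 35 per arm almost never reach P<0.05 under Fisher's test.
- Uncorrected chi-square on every binary outcome would reach 53% in the high set. That means applying it to sparse tables and leaving the named Fisher test unused, which does not fit a plan that uses each where appropriate.

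The outcomes are also plainly dependent (birthweight with LGA, for example). Under the mixed rule, correlation of 0.5 to 0.7 brings the figures down to 28% to 37%.

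It is also fair to say that the event rates are assumed, that some outcomes read as safety outcomes for which stricter thresholds would be unwelcome, and that the results are not in these documents, so no misleading secondary claim has been shown. These points argue for labelling rather than alpha adjustment. They do not remove the rule.

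**Conclusion.** The point holds as a matter of labelling and interpretation. As written, any of 17 secondary outcomes with unadjusted two-sided P<0.05 is called statistically significant. If all 17 null hypotheses are true, the chance of at least one such result is about 18% to 44%; the middle set with independent tests gives 30% to 42%, with 0.35 to 0.54 expected.

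This rests on 35 per arm, the assumed event rates, latent correlation from 0 to 0.7, and Fisher throughout or chi-square only where expected counts are at least 5. The documents supply neither rates nor correlations, so the size is illustrative. The textual finding does not depend on it.

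The documents do not support any inference that the primary test's error rate is inflated: there is one primary outcome, tested at its own 5%. It is a cheap improvement that changes what may be concluded from the secondary results.

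**What to change.** In the analysis section:

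1. Restrict the P<0.05 significance claim to the first neonatal glucose.
2. Label all 17 secondary outcomes exploratory.
3. Report each secondary outcome as a between-group difference with a 95% confidence interval: a mean or risk difference, or a location difference where the Wilcoxon test is used. State that the intervals are not adjusted for multiplicity and that no significance claims are made from them.
4. Continue to report safety-type outcomes (for example ketoacidosis, ICU admission, maternal hypoglycemia) in full, with their estimates and intervals.

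The cost is a few sentences and a relabelled table. No new data are needed, so it can be done at reporting. The downside is that secondary results lose the significant label.
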